## 9.5 Selection of Subjects to be Included in the Analyses

**Screened Set** – The set of subjects who have signed informed consent.

**Enrolled Set** – Subjects who have signed informed consent and have begun some study procedures (eg, dispensed investigational product, current drug has been withdrawn).

**Safety Analysis Set 1** – Enrolled subjects who have taken 1 dose of investigational product in Part 1 and who have completed at least 1 follow-up safety assessment.

**Safety Analysis Set 2** – Enrolled subjects who have taken 1 dose of investigational product in Part 2 or Part 3 and who have completed at least 1 follow-up safety assessment.

It is noted that safety assessments from the period when a subject is exposed to calcium carbonate will be summarized for calcium carbonate treatment. Safety assessments from the

period when a subject is exposed to lanthanum carbonate will be summarized for lanthanum carbonate treatment.

**Safety Completer Set (SCS)** – Subjects who receive at least 8 weeks of lanthanum carbonate treatment from either Part 2 or Part 3 of the study.

**Full Analysis Set (FAS)**–Subjects who have taken at least 1 dose of investigational product and who have at least 1 phosphate assessment during Part 2 or Part 3.

**Per-protocol Set 1 (PP1)** – Subjects in the Full Analysis Set who complete 8 weeks of calcium carbonate treatment followed by 8 weeks of lanthanum carbonate treatment and who have serum phosphate assessment data available to allow summarizing the percentage of subjects achieving age-specific KDOQI target. Only subjects who have serum phosphate levels equal to or above the age-specific KDOQI targets at study entry and between the calcium carbonate treatment and lanthanum carbonate treatment at Visit 2.4 will be included in this set.

**Per-protocol Set 2 (PP2)** – Subjects in the Full Analysis Set who complete 8 weeks of treatment with lanthanum carbonate and who have serum phosphate assessment data available to allow summarizing the percentage of subjects achieving age-specific KDOQI target. Subjects who have serum phosphate levels equal to or above the age-specific KDOQI targets prior to the start of lanthanum carbonate treatment will be included in this set.

**Pharmacokinetic Set 1** - Subjects in the Safety Analysis Set 1 for whom the primary pharmacokinetic data are considered sufficient and interpretable. Subjects in Part 1 who vomited may be excluded from Pharmacokinetic Set 1.

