#### **4.6 Per-protocol Set 2 (PP2)**

Per-protocol Set 2 is defined as subjects in the Full Analysis Set who complete 8 weeks of treatment with lanthanum carbonate and who have serum phosphate assessment data available to allow summarizing the percentage of subjects achieving age-specific KDOQI target. Subjects who have serum phosphate levels above the age-specific KDOQI targets prior to the start of lanthanum carbonate treatment will be included in this set. Further details are described in the Evaluable Subjects Determination Plan which can be found in Section 21.

Subjects who experienced hypophosphatemia, that lead to temporary interruption or discontinuation of treatment before the 8-week phosphate assessment, are considered compliant with the 8 week treatment requirement (as treatment dosed per-protocol, Section 6.2.1) and can thus be included in the PP2, PP1, and SCS analysis populations.

In previous versions of the protocol, a Per-protocol (PP) Set, defined as consisting "... of all Subjects in the FAS who complete Part 2 (ie, subjects who have a visit 2.8 serum phosphorus assessment) and do not have any pre-defined major protocol deviations that may affect the primary efficacy variable" was the only analysis set created to summarize efficacy endpoints. Following Protocol Version 6.0 (Amendment 5), two PP sets: PP1 and PP2 were defined.

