## 21. APPENDIX

### 21.1 Evaluable Subject Determination Plan

#### 1. Definition of Evaluable Subject in Per-Protocol Analysis Set 2 for Primary Endpoint Assessment

For the purposes of the primary endpoint assessment, at least 32 subjects, who complete 8 weeks of treatment with lanthanum carbonate and are assessable for baseline and 8 weeks serum phosphate level, will be required. Approximately 65 subjects may be enrolled to acquire at least 32 evaluable subjects. In order to prevent over enrolment, subjects' evaluability status will be assessed and confirmation of achieving at least 32 evaluable subjects will be performed.

The criteria that subjects must meet to determine eligibility include:

- Aged 10 years to <18 years of age at the time of consent
- Confirmed serum phosphorus level drawn prior to commencing Lanthanum therapy in Part 2 or Part 3 of the clinical trial (Baseline Phosphorus)
  - Subjects who participated in Part 2a and received calcium carbonate, baseline serum phosphorus must be drawn after a washout period of up to 3 weeks
- Baseline serum phosphorus levels above KDOQI recommendations:
  - Age <12 years: Serum phosphorus >6.0mg/dL (1.94mmol/L)
  - Age ≥12 years and older: Serum phosphorus >5.5mg/dL (1.78mmol/L)
- Demonstration of 8 weeks of Lanthanum therapy
- Confirmed serum phosphorus level after 8 weeks of Lanthanum therapy
- Both baseline and 8 weeks serum phosphorus levels are assessed at the same lab (central or local lab)
- Subjects, who received lanthanum carbonate therapy in part 2 or part 3 but did not receive 8 weeks of continuous treatment because of temporary dose interruption due to hypophosphatemia (protocol Appendix 2: guidelines for phosphorus and calcium levels), will be considered evaluable, if they satisfy other criteria mentioned above (eg baseline phosphate > KDOQI target).

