## IV. Post 8-week Phosphate Level:

- i) Subset week 8 central lab data from Part 2 or Part 3 central lab data, selecting the on-treatment record closest to target day 56/week 8 (with +/-7 days window). Target day is created using the first dose of Lanthanum in Part 2 or Part 3 (if Part 2 first Lanthanum dose is missing).
- ii) Subset week 8 local lab data from Part 2 or Part 3 local lab data, select the on-treatment record closest to target day 56/week 8 (with +/-7 days window). Target day is created using the first dose of Lanthanum in Part 2 or Part 3 (if Part 2 first Lanthanum dose is missing).
- iii) For subjects who experienced hypophosphatemia, that lead to temporary interruption or discontinuation of treatment before the 8 weeks phosphate assessment they will be considered compliant with the 8 weeks treatment requirement.

In the case of missing central lab data, local lab data will be used. Serum phosphorous assessments must come from a homogeneous source ie, from either central or local lab for baseline and following weeks 8 of lanthanum treatment, respectively, within subject.

If baseline phosphorus value from central lab is available and above the KDOQI criteria, but the central lab 8-week value is missing, then local lab data (baseline and day 56/week 8 phosphorus results) can be used.

NB. Both the baseline and day 56/week 8 phosphorus results must come from a single source (both central or both local).

If baseline phosphorus value from central lab is available and not above the KDOQI criteria, then the subject is not evaluable even if the subject has local lab values for both baseline and 8-week and the baseline value satisfies KDOQI criteria. Evaluability based on local lab is assessed only if central laboratory data is missing.

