## 1.2 Data Sources for Assessment of Evaluability

Evaluability Assessment will be performed on the subject level analysis data set (one record per subject) created through the steps described in section V.

Evaluability is determined if the following conditions are met

1. If subject is not a screen failure
2. Baseline Phosphate data is not missing, and baseline phosphate is  $\geq$  KDOQI Target
3. Week 8 Phosphate data is not missing

OR

Phosphate value missing at Week 8, but early termination shows hypophosphatemia (Protocol Appendix 2: guidelines for phosphorus and calcium levels).

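### The primary set PP2 admits early stops with low phosphate but not early removals with high phosphate, and the scoring of those admitted is not stated

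*SAP*

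**What the plan says.** Protocol Section 9.5 makes PP2 a completer set: "Subjects in the Full Analysis Set who complete 8 weeks of treatment with lanthanum carbonate and who have serum phosphate assessment data available". Protocol 9.10.1 names the FAS and PP2 together for the primary endpoint and leaves missing-data handling to the SAP. SAP Section 10.1 makes PP2 the primary population. The result is one percentage with an exact (Clopper-Pearson) 95% interval, and the target has an upper limit only.

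The SAP then deals with low phosphate in four places:

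- **Section 4.6.** Subjects whose hypophosphatemia led to events "that lead to temporary interruption or discontinuation of treatment before the 8-week phosphate assessment, are considered compliant with the 8 week treatment requirement", and they "can thus be included in the PP2, PP1, and SCS analysis populations". The same section still asks for subjects "who have serum phosphate assessment data available to allow summarizing the percentage of subjects achieving age-specific KDOQI target".
- **Section 21.1, item 1.** A confirmed level after 8 weeks of lanthanum is on the list of criteria. The exception is for subjects who "did not receive 8 weeks of continuous treatment because of temporary dose interruption due to hypophosphatemia"; they "will be considered evaluable, if they satisfy other criteria mentioned above".
- **Section 21.1, item 1.1 IV.** The Week 8 value is found by "selecting the on-treatment record closest to target day 56/week 8 (with +/-7 days window". For low phosphate, only the treatment requirement is waived.
- **Section 21.1, item 1.2.** A Week 8 value must be present, or else "Phosphate value missing at Week 8, but early termination shows hypophosphatemia". No other reason for a missing value is accepted.

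Protocol 4.4.1 and Appendix 2 require removal when phosphorus rises above 10.0 mg/dL outside washout. The SAP has no evaluability rule for those subjects.

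**The concern.** Whether a subject who stops early counts in the primary denominator depends on that subject's phosphate. A low value at termination lets the subject in. A value above 10.0 mg/dL gives no way in. Phosphate also decides whether the target is met, so the set is partly selected on the outcome. The primary analysis has no comparator arm in which a similar selection might cancel.

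There are two further problems. Items 1 and 1.2 of the appendix give different answers for a subject who terminates with low phosphate and no Week 8 value, so two programmers could build different PP2 sets. And nothing in the supplied text says whether that subject counts as achieved, not achieved or missing.

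**Working it through.** **The plan's own figure.** The documents give no expected percentage at target and no number of early stops. The only anchor is the 32 evaluable subjects in SAP 2.5, justified by the chance of seeing at least one event at a true rate of 5%: 1 − 0.95^32 = 80.6%, as stated. The protocol's 35 gives 1 − 0.95^35 = 83.4%, also as stated. Neither is in dispute.

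**Can a high-phosphate removal miss the window?** Part 2b titration samples are taken at Weeks 2, 4 and 6, each ±3 days (Protocol 7.1.2.7). The latest is day 42 + 3 = 45. The Week 8 window is day 56 ± 7, so days 49 to 63, and the record must be on treatment. A removal prompted by any titration visit therefore leaves no Week 8 value. A removal on a sample inside the window can still enter through the ordinary condition, so the gap concerns earlier removals.

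**Is a low-phosphate termination value at target?** The Appendix 2 limits are below 4.0 and 3.5 mg/dL at 12 to <18 years, and below 4.5 and 4.0 mg/dL at 10 to <12 years. The targets are ≤5.5 and ≤6.0 mg/dL. Any value meeting those limits is below target.

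**Size, with assumed counts.** Let W = 30 subjects have a Week 8 value, x = 15 of them at target, L = 1 or 2 admitted low-phosphate stops, and H = 1 to 3 early removals above 10.0 mg/dL.

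*Effect of the exception, against the completer rule x/W = 15/30 = 50.0%:*

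| Scoring of admitted subjects | L = 1 | L = 2 |
|---|---|---|
| Achieved, (x+L)/(W+L) | 16/31 = 51.6% (+1.6) | 17/32 = 53.1% (+3.1) |
| Not achieved, x/(W+L) | 15/31 = 48.4% (−1.6) | 15/32 = 46.9% (−3.1) |
| Left out of the denominator, x/W | 50.0% (0) | 50.0% (0) |

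Scored as achieved, the shift is +2.3 to +4.4 points if x = 9 (10/31 and 11/32 against 30.0%), and +1.0 to +1.9 if x = 21 (22/31 and 23/32 against 70.0%).

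*Effect of leaving out high-phosphate removals, with no exception at all, x/W against x/(W+H):* 15/30 = 50.0% against 15/31 = 48.4%, 15/32 = 46.9% and 15/33 = 45.5%. The differences are 1.6, 3.1 and 4.5 points, or about 1.5 per removal. For one removal the difference is 1.0 point at x = 9 (9/30 against 9/31) and 2.3 at x = 21 (21/30 against 21/31).

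*Both together, L = 2 and H = 3, low stops scored as achieved:*

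| Rule | Result | Exact 95% interval |
|---|---|---|
| SAP item 1.2 | 17/32 = 53.1% | 34.7 to 70.9 |
| Keep both kinds of stop | 17/35 = 48.6% | 31.4 to 66.0 |
| Drop both (completer rule) | 15/30 = 50.0% | 31.3 to 68.7 |

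The half-width of the first interval is (70.9 − 34.7)/2 = 18.1 points. With L = H = 0 all three rules agree.

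**The case against.** The case for leaving the plan alone has real substance.

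- **The completer rule is the protocol's.** In the last table the SAP rule exceeds keeping both by 4.6 points, and a reader might blame the exception for all of it. The documents do not support that: with the exception deleted, three high-phosphate removals still make a difference of 4.5 points (15/30 against 15/33). What the exception adds is its shift against the completer rule. This stands.
- **The SAP gives a reason.** Section 4.6 says these subjects were dosed according to the protocol. That is a recognisable per-protocol argument for waiving the treatment requirement. It does not explain waiving the Week 8 value.
- **Section 4.6 does not plainly contradict item 1.2.** It asks for phosphate data without naming Week 8, and it mentions discontinuation. A termination value could satisfy it. The clear conflict is between items 1 and 1.2.
- **The case may be rare.** Low phosphate is not a stopping criterion in Protocol 4.4.1; Section 6.2.1 handles it by interrupting and resuming the binder. There may be no such terminations. This stands.
- **The scoring may be written elsewhere.** Table specifications are in a separate document (SAP Section 1), and item 1.2 refers to a section V that the supplied appendix does not show. So one can say only that the supplied text is silent. Since the protocol assigns missing-data rules to the SAP, that is where the rule should be found.
- **Other outputs help.** Target achievement by week (Tables 3.1.8.1 and 3.1.8.2), withdrawals by reason and the listing of evaluable subjects would let a reader trace these subjects. They do not settle the primary denominator. FAS Table 3.1.1.2 has no stated rule for a missing Week 8 value either.

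**Conclusion.** The point holds in a limited form. SAP 21.1 item 1.2 adds to the protocol's completer set an exception open to one direction of phosphate only, conflicts with item 1, and leaves the admitted subject unscored in the supplied text.

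On the natural reading (target achieved), one or two such stops raise the primary percentage by 1.6 to 3.1 points, assuming 15 of 30 at target. Separately, each early removal above 10.0 mg/dL that is left out is worth about 1.5 points against counting it as not achieved; that part comes from the protocol's own definition. All counts are assumptions.

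A reader might infer that the exception is bound to inflate the result. It is not: scored as not achieved, it lowers the percentage by the same 1.6 to 3.1 points against the completer rule, so its direction is open until the scoring is written down. The shifts are small beside a half-width of about 18 points, and the analysis is descriptive, so what is affected is the estimate and its reading, not a test. It should still be fixed, because a rule that selects on the outcome is avoidable and cheap to correct. No clinical stopping rule is questioned.

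**What to change.** Before database lock:

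1. Reconcile items 1 and 1.2 of SAP 21.1, and align Section 4.6, item 1.1 IV and the PP1 text in item 2 with the result, so that both kinds of early stop are treated alike in the primary percentage. There are two ways. Either use actual Week 8 values only, which is the protocol's completer rule; or keep the exception, scored on the termination value, and count removals above 10.0 mg/dL as not achieved. Report the version not chosen as a sensitivity line.
2. State how subjects with no Week 8 value enter FAS Table 3.1.1.2, with removals above 10.0 mg/dL counted as not achieved.
3. List in Section 17 any exception that is kept, its scoring, and the choice of PP2 as primary. Section 17 now lists a different change to the PP definitions but none of these.

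The cost is SAP wording and one or two table lines. Termination assessments (Protocol Table 3, footnote c) and reasons for stopping (Protocol 4.4.2) are already collected. The reported percentage may be slightly lower. Each way also has its own price. Under the first, anyone admitted only through the exception no longer counts towards the 32. The second puts non-completers into a set the protocol limits to completers, so it must be declared as a departure.

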## 2. Definition of Evaluable Subjects in Per-Protocol Analysis Set 1 for Primary Endpoint Assessment

Evaluable subjects in per-protocol 1 population will be defined similar to evaluable subject in per-protocol 2 population, see above, with subjects meeting the following criteria to be deemed eligible for the per-protocol 1 population:

- Aged 10 years to <18 years of age at the time of consent
- Confirmed serum phosphorus level at study entry and between the calcium carbonate treatment and lanthanum carbonate treatment at Visit 2.4 or unscheduled visits in part 2 (Baseline Phosphorus)
  - Subjects who participated in Part 2a and received calcium carbonate, baseline serum phosphorus must be drawn after a washout period of up to 3 weeks
- Baseline serum phosphorus levels above KDOQI recommendations:
  - Age <12 years: Serum phosphorus >6.0mg/dL (1.94mmol/L)
  - Age  $\geq$ 12 years and older: Serum phosphorus >5.5mg/dL (1.78mmol/L)
- Demonstration of 8 weeks of Calcium Carbonate therapy followed by 8 weeks of Lanthanum therapy
- Confirmed serum phosphorus level after 8 weeks of Calcium Carbonate therapy followed by 8 weeks of Lanthanum therapy
- Both baseline and 8 weeks serum phosphorus levels are assessed at the same lab (central or local lab)

- Subjects, who received Calcium Carbonate and Lanthanum Carbonate therapy in part 2 or part 3 but did not receive 8 weeks of continuous treatment because of temporary dose interruption due to hypophosphatemia (protocol Appendix 2: guidelines for phosphorus and calcium levels), will be considered evaluable, if they qualify other criteria mentioned above (eg baseline phosphate > KDOQI target).
